9.1 Source and Timing of Biospecimen Collections

Details on the collection, storage, processing, handling, and shipping are provided in the Laboratory Manual.

Plasma for Pharmacokinetic Measurements

Phase 1 and Phase 2

- Cycle 1 Day 1 (predose, 2-4 hour postdose)
- Cycle 1 Day 15 (predose, 2-4 hour post dose)
- Cycle 2 Day 15 (predose, a postdose sample any time during the clinical visit)
- Cycle 3 Day 15 (predose, a postdose sample any time during the clinical visit)
- Cycle 4 Day 15 (predose, a postdose sample any time during the clinical visit)

Plasma collected for TAK-659 PK measurements may additionally be used for exploratory measurement of metabolites of TAK-659, if technically feasible and considered necessary for further understanding the metabolism and clearance of TAK-659.

Bone Marrow Aspirate for Biomarker Analyses

Bone marrow aspirate will be collected for translational laboratory pharmacodynamic analysis, qPCR, in vitro analyses, proteomic assays via Western blotting, and MRD via digital PCR. Bone marrow aspirate samples will be collected at the following timepoints:

Phase 1

- Screening,
- Cycle 1 Day 4 or Day 8: Day 4 collection for the 1st 5 patients. Depending on timing of index peripheral blood reduction, collection may be moved to day 8 for subsequent patients.
- Cycle 1 Day 15
- Cycle 2 Day 15
- Cycle 4 Day 15

Phase 2

- Screening
- Cycle 1 Day 4 or Day 8: depending on findings from Phase I patients.
- Cycle 1 Day 15
- Cycle 3 Day 22 (or within 3 days prior to C4D1)*
- Progression

Note: In cases when insufficient bone marrow aspirate is collected, peripheral blood will be collected and submitted per the instructions in the CLM.

**In the case of post-Cycle 3 assessment, aspirate and biopsy are suggested on day 22 (or within 3 days prior to C4D1), simultaneous with the plan to continue onto Cycle 4 day 1 that same day following the procedure, so to serve as record establishing the optimal response/composite CR. Such planning should be guided by the trend of blast reduction observed during Cycles 1, 2.*

Buccal Swabs for Germline DNA**Phase 1 and Phase 2**

- Pre-treatment Cycle 1 Day 1

Serum for Proteomic Analysis**Phase 1 and Phase 2**

- Pre-treatment Cycle 1 Day 1
- Cycle 1 Day 4 or Day 8: collection day will correspond to BM aspirate

9.1.1 Banking of Leftover Biospecimens

Subject consent will be obtained to bank any leftover samples collected for study-specific correlative research. Hoosier Cancer Research Network (HCRN), as Administrative Headquarters for the Big Ten CRC, will manage the banked samples. Samples will be banked indefinitely in the Hoosier Cancer Research Network Biorepository and used for future unspecified cancer-related research.

9.1.2 Banking Samples for Future Unspecified Research

Subject consent will be obtained to collect additional samples for future unspecified Big Ten Cancer Research Consortium studies. HCRN will manage the banked samples. Samples will be banked indefinitely in the HCRN Biorepository.

This includes:

- Whole blood: Whole blood will be collected prior to treatment on Cycle 1 Day 1.
- Pre- and Post-treatment plasma: Whole blood for plasma will be collected prior to treatment on Cycle 1 Day 1 and at the 30-day Safety Follow-up visit.
- Pre- and Post-treatment serum: Whole blood for serum will be collected prior to treatment on Cycle 1 Day 1 and at the 30-day Safety Follow-up visit.

Please refer to the Correlative Laboratory Manual (CLM) for all sample collection, processing, labeling, and shipping instructions.

9.1.3 Confidentiality of Biospecimens

Samples will be identified by a subject's study number assigned at the time of registration to the trial. Any material issued to collaborating researchers will be anonymized and only identified by the subject's study number.

10. CRITERIA FOR DISEASE EVALUATION

Assessment of disease response will follow the criteria outlined in the Revised Recommendations of the International Working Group (IWG) for Diagnosis, Standardization of Response Criteria, Treatment Outcomes, and Reporting Standards for Therapeutic Trials in Acute Myeloid Leukemia. (34) Investigators are encouraged to consult the reference for more detailed explanation of response criteria.

CR, CRi/CRp, and PR are defined using the following criteria:

Morphologic CR: A CR designation requires that the patient achieve the morphologic leukemia-free state and have an ANC of more than 1,000/uL and platelets of \geq 100,000/uL. A morphologic leukemia-free state requires less than 5% blasts in an aspirate sample with marrow spicules and with a count of at least 200 nucleated cells. There should be no blasts with Auer rods. Hemoglobin concentration or hematocrit has no bearing on remission status, although the patient must be independent of transfusions. There should be no residual evidence of extramedullary leukemia.

Morphologic CRi, CRp: After chemotherapy, some patients fulfill all of the criteria for CR except for residual neutropenia ($<1,000/\mu\text{L}$) or thrombocytopenia ($<100,000/\mu\text{L}$).

PR: This designation requires all of the hematologic values for a CR but with a decrease of at least 50% in the percentage of blasts to 5% to 25% in the bone marrow aspirate. Thus, if the pretreatment bone marrow blast percentage was 50% to 100%, the percentage of blasts must decrease to a value between 5% to 25%; if the pretreatment blast percentage was 20% to less than 49%, they must decrease by at least half to a value of more than 5%. A repeat bone marrow aspiration after several weeks may be required to distinguish between a PR and increased blasts caused by bone marrow regeneration. A value of $\leq 5\%$ blasts may also be considered a PR if Auer rods are present.

Progressive Disease

Because the IWG criteria for AML do not provide a standardized definition for progressive disease,⁽¹²⁾ in this protocol, progressive disease is defined as 1 of the following:

- $>50\%$ increase in bone marrow blasts from baseline value.
- $>50\%$ increase in circulating blasts from baseline value with absolute blast count $> 1000/\text{mm}^3$
- Development of biopsy-proven extramedullary disease, or new sites of extramedullary leukemia.

Note: If the initial marrow blast percentage is too high to base progression on a >50% increase in bone marrow blasts, then peripheral blood criteria will be used.

11. DRUG INFORMATION

11.1 TAK-659

11.1.1 Supplier/How Supplied

TAK-659 has been formulated into immediate-release film-coated tablets for use in phase 1 clinical studies via a common granulation process. Three different tablet dosage strengths, 20 mg, 60 mg, and 100 mg, were formulated. The formulation contains compendial excipients that include mannitol, microcrystalline cellulose, hydroxypropyl cellulose, sodium starch glycolate, and magnesium stearate. Tablets were coated with Opadry® film coat.

TAK-659 20 mg, 60 mg, and additional dose strength tablets will be packaged into round, white, high-density polyethylene (HDPE) bottles with induction seal, desiccant pack, and polypropylene child resistant caps. Each bottle containing 30 tablets of TAK-659 will be labeled with either a single-panel or multi-language label containing pertinent study information, country-specific requirements, and a caution statement.

Takeda will supply TAK-659 at no charge to subjects participating in this clinical trial.

The investigator shall take responsibility for and shall take all steps to maintain appropriate records and ensure appropriate supply, storage, handling, distribution, and usage of investigational product in accordance with the protocol and any applicable laws and regulations.

11.1.2 Storage and Stability

TAK-659 tablets should be stored in the original dispensing bottles at 1°C to 25°C (33.8°F-77°F) with excursions permitted to 30°C (86°F) as long as they do not exceed 7 days. All temperature excursions of the tablets must be reported back to the manufacturer for assessment and determination for continued use. The TAK-659 tablets must be used before the retest date indicated on the label and/or accompanying documentation. Throughout the duration of the clinical trial, the stability of the drug product will be monitored. TAK-659 tablets should remain in the original bottle provided to the investigational TAK-659 site and patients. Drug supply must be kept in an appropriate, limited access, secure place until it is dispensed to the enrolled patients.

Since TAK-659 is an investigational agent, it should be handled with due care. In the case of broken tablets, raising dust should be avoided during the clean-up operation. Damaged tablets may be harmful by inhalation, ingestion, or skin and/or eye contact. In the case of contact of damaged tablets with the eyes or skin, there should be immediate and thorough flushing and washing for at least 15 minutes with water (and soap for skin). Medical personnel should be notified.

Patients are to be instructed on proper storage, accountability, and administration of TAK-659, including that TAK-659 is to be taken as intact tablets.

A study drug accountability log must be completed for all study drug dispensed and administered to study patients.

11.1.3 Handling and Disposal

Patients should be instructed to return their empty blister packs to the investigative site, rather than discarding them. Reconciliation will occur accordingly when the patient returns for their next cycle of take-home medication.

11.1.4 Dispensing

TAK-659 must be dispensed only from official study sites and to eligible subjects under the supervision of the site investigator. TAK-659 must be stored in a secure area according to local regulations. The investigative site is responsible for dispensing TAK-659 in the correct daily dose configurations. Comprehensive instructions should be provided to the patient in order to ensure compliance with dosing procedures. Patients who are receiving take-home medication must be given only 1 cycle of medication at a time.

11.1.5 Packaging and Labeling

TAK-659 20 mg, 60 mg, 100 mg, and additional dose strength tablets will be packaged into round, white, high-density polyethylene (HDPE) bottles with induction seal, desiccant pack, and polypropylene child resistant caps. Each bottle containing 30 tablets of TAK-659 will be labeled with either a single-panel or multilanguage label containing pertinent study information, country-specific requirements, and a caution statement.

11.1.6 Adverse Events

See summary of adverse events in section 1.4.6. Please also reference the current TAK-659 IB for a comprehensive list of adverse events.

11.2 Ixazomib

Ixazomib is a reversible proteasome inhibitor. Ixazomib preferentially binds and inhibits the chymotrypsin-like activity of the beta 5 subunit of the 20S proteasome.

Ixazomib induced apoptosis of multiple myeloma cell lines in vitro. Ixazomib demonstrated in vitro cytotoxicity against myeloma cells from patients who had relapsed after multiple prior therapies, including bortezomib, lenalidomide, and dexamethasone. The combination of ixazomib and lenalidomide demonstrated synergistic cytotoxic effects in multiple myeloma cell lines. In vivo, ixazomib demonstrated antitumor activity in a mouse multiple myeloma tumor xenograft model.

11.2.1 Supplier/How Supplied

Ixazomib will be supplied by Takeda Oncology at no charge to patients participating in this clinical trial. The ixazomib drug product will be from investigational supply.

The investigator shall take responsibility for and shall take all steps to maintain appropriate records and ensure appropriate supply, storage, handling, distribution, and usage of investigational product in accordance with the protocol and any applicable laws and regulations.

11.2.2 Description of Investigational Agent

The ixazomib drug product is provided in strengths of 4.0-, 3.0-, and 2.3-mg capsules as the active boronic acid. The dose strengths are differentiated by both capsule size and color as described below:

Dose Strength	Capsule Size	Capsule Color
4.0 mg	Size 4	Ivory
3.0 mg	Size 3	Light gray
2.3 mg	Size 2	Light pink

For additional details, please see the ixazomib IB.

11.2.3 Storage and Stability

Upon receipt at the investigative site, ixazomib should remain in the blister and carton provided until use or until drug is dispensed. Ixazomib should be stored at the investigative site between +2°C and +30°C (35.6°F-86°F). Do not freeze ixazomib or store above 30°C. Any extreme in temperature should be reported as an excursion and should be dealt with on a case-by-case basis.

11.2.4 Handling and Disposal

Ixazomib is a cytotoxic drug. Follow applicable special handling and disposal procedures. Do not open or crush capsules. Avoid direct contact with the capsule contents. In case of capsule breakage, avoid direct contact of capsule contents with the skin or eyes. If contact occurs with the skin, wash thoroughly with soap and water. If contact occurs with the eyes, flush thoroughly with water.

Any unused medicinal product or waste material should be disposed in accordance with local requirements.

11.2.5 Dispensing

Ixazomib must be dispensed only from official study sites and to eligible subjects under the supervision of the site investigator. Ixazomib should be stored in a secure area according to local regulations. It is the responsibility of the site investigator to ensure that study drug is only dispensed to subjects.

11.2.6 Adverse Events

The most common adverse events associated with ixazomib are thrombocytopenia, gastrointestinal toxicity (diarrhea, constipation, nausea, and emesis), peripheral neuropathy, peripheral edema, and cutaneous reactions. Please see the current IB for the comprehensive list of adverse events.

12. ADVERSE EVENTS

12.1 Definitions

12.1.1 Adverse Event (AE)

An AE is any untoward medical occurrence whether or not considered related to the study drug that appears to change in intensity during the course of the study. The following are examples of AEs:

- Unintended or unfavorable sign or symptom
- A disease temporally associated with participation in the protocol
- An intercurrent illness or injury that impairs the well-being of the subject

Abnormal laboratory values or diagnostic test results constitute AEs only if they induce clinical signs or symptoms or require treatment or further diagnostic tests

Hospitalization for elective surgery or routine clinical procedures that are not the result of an AE (e.g., surgical insertion of central line) should not be recorded as an AE.

Disease progression should not be recorded as an AE, unless it is attributable to the study regimen by the site investigator.

12.1.2 Serious Adverse Event (SAE)

An SAE is an adverse event that:

- Results in death. NOTE: Death due to disease progression should not be reported as a SAE, unless it is attributable by the site investigator to the study drug(s)
- Is life-threatening (defined as an event in which the subject was at risk of death at the time of the event; it does not refer to an event which hypothetically might have caused death if it were more severe)
- Requires inpatient hospitalization for >24 hours or prolongation of existing hospitalization.
NOTE: Hospitalization for anticipated or protocol specified procedures such as administration of chemotherapy, central line insertion, metastasis interventional therapy, resection of primary tumor, or elective surgery, will not be considered serious adverse events.
- Results in persistent or significant disability/incapacity
- Is a congenital anomaly or birth defect
- Is an important medical event (defined as a medical event(s) that may not be immediately life-threatening or result in death or hospitalization but, based upon appropriate medical and scientific judgment, may jeopardize the subject or may require intervention (e.g., medical, surgical) to prevent one of the other serious outcomes listed in the definition above). Examples of such events include, but are not limited to, intensive treatment in an emergency room or at home for allergic bronchospasm; blood dyscrasias or convulsions not resulting in hospitalization; or the development of drug dependency or drug abuse.
- New primary malignancy
- Pregnancy

12.1.3 Unexpected Adverse Event

For this study, an AE is considered unexpected when it varies in nature, intensity or frequency from information provided in the current IB, package insert, or when it is not included in the informed consent document as a potential risk. Unexpected also refers to AEs that are mentioned in the IB as occurring with a class of drugs or are anticipated from the pharmacological properties of the drug but are not specifically mentioned as occurring with the particular drug under investigation.

12.1.4 Relatedness

AEs will be categorized according to the likelihood that they are related to the study drug(s). Specifically, they will be categorized using the following terms:

Unrelated	The Adverse Event is not related to the drug(s)
Unlikely	The Adverse Event is doubtfully related to the drug(s)
Possible	The Adverse Event may be related to the drug(s)

Probable	The Adverse Event is likely related to the drug(s)
Definite	The Adverse Event is clearly related to the drug(s)

12.2 Reporting

12.2.1 Adverse Events

- AEs will be recorded from time of signed informed consent until 30 days after discontinuation of study drug(s).
- AEs will be recorded regardless of whether or not they are considered related to the study drug(s).
- All AEs will be recorded in the subject's medical record and on the appropriate study specific eCRF form within the EDC system.
- All AEs considered related to study drug(s) will be followed until resolution to \leq Grade 1 or baseline, deemed clinically insignificant, and/or until a new anti-cancer treatment starts, whichever occurs first.

12.2.2 Serious Adverse Events (SAEs)

12.2.2.1 Site Requirements for Reporting SAEs to Big Ten CRC Administrative Headquarters

- SAEs will be reported from time of signed informed consent until 30 days after discontinuation of study drug(s).
- SAEs will be reported on the SAE Submission Form and entered in the SAE tab in the EDC system **within 1 business day** of discovery of the event.
- SAEs include events related and unrelated to the study drug(s).
- All SAEs will be recorded in the subject's medical record and on the appropriate study specific eCRF form within the EDC system.
- All SAEs regardless of relation to study drug will be followed until resolution to \leq Grade 1 or baseline and/or deemed clinically insignificant and/or until a new anti-cancer treatment starts, whichever occurs first.

The site will submit the completed SAE Submission Form (see the Documents/Info tab of the EDC) to Big Ten CRC AHQ within **1 business day** of discovery of the event. The form will be sent electronically to Big Ten CRC AHQ at [contact]. The site investigator is responsible for informing the IRB and/or other local regulatory bodies of the SAE as per local requirements.

The original copy of the SAE Submission Form and the email correspondence must be kept within the study file at the study site.

Once the SAE has resolved, sites must electronically submit a follow up SAE Submission Form within a reasonable timeframe to Big Ten CRC AHQ at [contact].

12.2.2.2 Site Requirements for Reporting Pregnancy and Birth Events to BTCRC Administrative Headquarters

If a woman becomes pregnant or suspects that she is pregnant while participating in this study or within 90 days after the last dose, she must inform the site investigator immediately and permanently

discontinue study drug. The site must immediately submit a completed Pregnancy Form to BTCRC AHQ at [contact]. The pregnancy must be followed for the final pregnancy outcome.

If a female partner of a male patient becomes pregnant during the male patient's participation in this study (i.e. from the initiation of study drug(s) through 90 days after the last dose of study drug), the site investigator must also immediately submit a completed Pregnancy Form to BTCRC AHQ at [contact]. Every effort should be made to follow the pregnancy for the final pregnancy outcome.

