 - a. Patients, if relapsed/ refractory, must have exposure to no more than 2 prior chemotherapy regimens. Re-induction with the same regimen or stem cell transplant will not be considered a separate regimen.
 - b. Patients must not have prior exposure to any investigational Flt3 inhibitors (midostaurin or gilteritinib are allowed)
7. Eastern Cooperative Oncology Group (ECOG) performance status 0-2
8. Life expectancy of greater than 3 months as determined by the treating physician.
9. Female patients who:
 - Are postmenopausal for at least 1 year before the screening visit, OR
 - Are surgically sterile, OR
 - If they are of childbearing potential, agree to practice 2 effective methods of contraception at the same time, from the time of signing the informed consent through 180 days after the last dose of study drug, or
 - Agree to practice true abstinence, when this is in line with the preferred and usual lifestyle of the subject. Periodic abstinence [eg, calendar, ovulation, symptothermal, postovulation methods], withdrawal, spermicides only, and lactational amenorrhea are not acceptable methods of contraception. Female and male condoms should not be used together.)
 - Agree not to donate eggs (ova) during the course of this study or 180 days after receiving their last dose of study drug.
10. Male patients, even if surgically sterilized (i.e., status post-vasectomy), who:
 - Agree to practice effective barrier contraception during the entire study treatment period and through 180 days after the last dose of study drug, or
 - Agree to practice true abstinence, when this is in line with the preferred and usual lifestyle of the subject. (Periodic abstinence [eg, calendar, ovulation, symptothermal, postovulation methods for the female partner] and withdrawal are not acceptable methods of contraception. Female and male condoms should not be used together.)
 - Agree not to donate sperm during the course of this study or within 180 days after receiving their last dose of study drug.
11. Voluntary written consent must be given before performance of any study related procedure not part of standard medical care, with the understanding that consent may be withdrawn by the patient at any time without prejudice to future medical care
12. In the absence of rapid progressive disease, the interval from prior systemic anticancer treatment to time of TAK-659/Ixazomib administration should be at least 2 weeks for cytotoxic agents

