5.8 Reproductive Considerations

It is not known what effects TAK-659 has on human pregnancy or development of the embryo or fetus. Therefore, female patients participating in this study should avoid becoming pregnant, and male patients should avoid impregnating a female partner. Nonsterilized female patients of reproductive age group and male patients should use effective methods of contraception through defined periods during and after study treatment as specified below.

Female patients must meet 1 of the following:

- Postmenopausal for at least 1 year before the screening visit, or
- Surgically sterile, or
- If they are of childbearing potential, agree to practice 1 highly effective methods of contraception and 1 additional effective (barrier) method, at the same time, from the time of signing of the informed consent form through 180 days(or longer, as mandated by local labeling [eg, USPI, SmPC, etc;]) after the last dose of study drug, or
- Agree to practice true abstinence, when this is in line with the preferred and usual lifestyle of the patient. (Periodic abstinence [eg, calendar, ovulation, symptothermal, postovulation methods], withdrawal, spermicides only, and lactational amenorrhea are not acceptable methods of contraception. Female and male condoms should not be used together.)
- Agree to not donate eggs (ova) during the course of this study or 180 days after receiving their last dose of study drug(s).

Male patients, even if surgically sterilized (i.e., status post-vasectomy) must agree to 1 of the following:

- Agree to practice highly effective barrier contraception during the entire study treatment period and through 180 days after the last dose of study drug, OR
- Agree to practice true abstinence, when this is in line with the preferred and usual lifestyle of the patient. (Periodic abstinence [eg, calendar, ovulation, symptothermal, postovulation methods for the female partner], withdrawal, spermicides only, and lactational amenorrhea are not acceptable methods of contraception. Female and male condoms should not be used together.)
- Agree not to donate sperm during the course of this study or 180 days after receiving their last dose of study drug.

Acceptable non-hormonal birth control methods:

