- Total sexual abstinence ie, refrain from any form of sexual intercourse in line with the patients' usual and/or preferred lifestyle. Abstinence must be for the total duration of the study treatment and for at least 1 month (for female patients) or 3 months (for male patients) after the last dose of study treatment.
- NOTE: Periodic abstinence (eg, calendar ovulation, symptothermal, post-ovulation methods) and withdrawal are not acceptable methods of contraception.
- Vasectomised sexual partner PLUS male condom. With participant assurance that partner received post-vasectomy confirmation of azoospermia.
- Tubal occlusion PLUS male condom
- Intrauterine Device PLUS male condom. Provided coils are copper-banded.

Acceptable hormonal methods:

- Etonogestrel implants (eg, Implanon®, Norplant®) PLUS male condom
- Normal and low dose combined oral pills PLUS male condom
- Hormonal shot or injection (eg, Depo-Provera) PLUS male condom
- Intrauterine system device (eg, levonorgestrel-releasing intrauterine system –(Mirena®) PLUS male condom

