6.6 Protocol Discontinuation

If a subject decides to withdraw from the study (and not just from protocol therapy) all efforts should be made to complete the final study assessments. The site study team should contact the subject by telephone or through a clinic visit to determine the reason for the study withdrawal. If the reason for withdrawal is an adverse event, it will be recorded on the eCRF.

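### Partner-pregnancy reporting ends 90 days after the last dose, but the protocol's own contraception period for male patients runs to 180 days

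*Combined protocol and SAP*

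**What the plan says.** **Precaution period.** Section 3.1 (items 9 and 10) and Section 5.8 set contraception to 180 days after the last dose for both sexes.

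- Women of childbearing potential who use contraceptive methods do so "from the time of signing the informed consent through 180 days after the last dose of study drug". Section 5.8 adds a possible extension: "through 180 days(or longer, as mandated by local labeling".
- Men must "Agree to practice highly effective barrier contraception during the entire study treatment period and through 180 days after the last dose of study drug", or practise true abstinence.
- Both sections bar egg and sperm donation for 180 days.

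**Reporting period.** Section 12.2.2.2 is shorter.

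- Partner pregnancy: a parenthesis introduced by i.e. spells out the male patient's participation as "from the initiation of study drug(s) through 90 days after the last dose of study drug".
- Female patient: if she becomes pregnant "while participating in this study or within 90 days after the last dose, she must inform the site investigator immediately".

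**Abstinence.** The true-abstinence options in Sections 3.1 and 5.8 give no duration. The only one stated is in the list of acceptable non-hormonal methods in Section 5.8: abstinence throughout treatment and "for at least 1 month (for female patients) or 3 months (for male patients) after the last dose of study treatment".

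**The concern.** The protocol treats 180 days after the last dose as the time when conception should be prevented, but for partners it stops collecting information halfway through. A partner who conceives on day 120, for example, does so while the patient is still bound to use contraception. Nothing in Section 12.2.2.2 then obliges the site to file a Pregnancy Form or follow the outcome.

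What is at stake is information on pregnancy outcomes. Section 5.8 concedes that "It is not known what effects TAK-659 has on human pregnancy or development of the embryo or fetus", and Section 1.4.7.1 reports TAK-659 as mutagenic in an Ames assay and aneugenic in micronucleus evaluations.

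Two neighbouring wordings raise related questions: how long reporting lasts for female patients, and whether the short abstinence minimums are meant to stand beside a 180-day rule for other methods.

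**Working it through.** No design quantity needs reproducing. The check compares the windows and adds a simple half-life calculation.

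**1. Partner window.** Contraception runs to day 180 (Sections 3.1 and 5.8) and reporting to day 90 (Section 12.2.2.2).

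180 − 90 = 90 days without a reporting duty.

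**2. Does anything else close the gap?**

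- Section 12.1.2 lists pregnancy as an SAE, but the SAE window in Section 12.2.2.1 ends 30 days after discontinuation, which is shorter still.
- Section 12.2.2.4 has headquarters pass on all pregnancy and birth events, but only after receiving a Pregnancy Form. Sites need not file one for a partner pregnancy after day 90.
- Section 8.7 lists survival, later anticancer therapy and, for patients who stop treatment in CR, progression. It does not mention pregnancy.

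None of these extends the window.

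**3. Female patients.** The result depends on what participating means.

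- If it includes the survival follow-up of up to 12 months (Sections 6.5 and 8.7), day 180 is covered while she remains in follow-up: gap 0 days. Section 6.6 supports this reading by separating study from treatment: "If a subject decides to withdraw from the study (and not just from protocol therapy".
- If it carries the meaning given for male patients in the next paragraph, reporting ends at day 90: gap 180 − 90 = 90 days.

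The range is 0 to 90 days.

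**4. Abstinence minimums.** Taking one month as 30 days:

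- Women: 180 − 30 = 150 days below the period for other methods.
- Men: 180 − 90 = 90 days below it.

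**5. Residual drug.** This assumes first-order decay at the terminal half-life.

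| Drug | Half-life | Five half-lives | Fraction left at day 30 | Fraction left at day 90 |
|---|---|---|---|---|
| Ixazomib (Section 1.5.3) | 9.5 days | 5 × 9.5 = 47.5 days | 2^−(30/9.5) = 0.112, about 11% | 2^−(90/9.5) = 0.0014, about 0.14% |
| TAK-659 (Section 1.4.2.1) | 34.4 hours | 5 × 34.4 = 172 h, about 7.2 days | not needed | not needed |

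The 1-month minimum for women is shorter than five ixazomib half-lives, and Section 11.2.4 describes ixazomib as cytotoxic. By day 90 both drugs are almost gone.

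**6. Scale.** The Synopsis plans 54 patients (18 + 36). Sections 5.1 and 5.3 allow replacements, so 54 is a planned total and not a ceiling. The documents give no expected number of pregnancies.

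**The case against.** **The windows need not match.** Contraception prevents and reporting observes, and no passage says the two periods must be equal. That is true, so this is a design weakness and not a broken rule. But the documents give no reason for stopping partner reporting at 90 days, and 180 days is the period the protocol itself chose, in two sections and for both sexes.

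**The drug is gone by then.** A reader might infer that conceptions in days 91 to 180 would be exposed to residual drug. The half-lives do not support that, and the case does not rest on it. It rests on the protocol's own precaution period, the genotoxicity findings and the unknown effects on pregnancy. Residual drug is relevant only to the 1-month abstinence minimum.

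**Late reports are hard to attribute.** Responders may go to transplant (Section 5.3.1), and later anticancer therapy is expected (Section 8.7). This limits what a late report can show. It does not justify leaving it out, because Section 12.2.2.2 does not make pregnancy reporting depend on causality.

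**The other two parts are not contradictions.** This stands. A reader might infer a definite 90-day gap for female patients too, but the wording may cover the whole follow-up. A reader might also infer that women are allowed unprotected exposure after one month. The figures are minimums, abstinence is offered only where it fits the patient's usual lifestyle, and a woman who stops abstaining could reasonably be held to the 180-day two-method option.

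**Unseen documents may settle it.** The Pregnancy Form is not included and the consent pages were removed. Either could address the period, so the finding applies to the protocol text as available.

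**Conclusion.** The partner-window mismatch is firm: 90 of the 180 post-dose contraception days carry no duty to report or follow a partner pregnancy, and no available passage supplies one. The female wording is an ambiguity worth 0 to 90 days. The abstinence minimums are unclear drafting, below the 180 days set for other methods, and the 1-month figure is the weaker because it falls short of 47.5 days.

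The half-life figures assume simple first-order decay and a 30-day month; the 90-day partner gap needs neither assumption. Few pregnancies are likely in a trial planned for 54 patients plus replacements. It would be wrong to infer any effect on the trial's results, since endpoints, sample size and error rates are untouched. This is a minor safety-reporting alignment, worth making because it is specific and cheap.

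**What to change.** - **Section 12.2.2.2, partners:** set the window from first dose through 180 days after the last dose.
- **Section 12.2.2.2, female patients:** state that reporting runs while participating and through at least 180 days after the last dose. A flat 180-day limit should be avoided, because it could shorten reporting if participating already includes the follow-up of up to 12 months. The words at least also leave room for the local-labeling extension in Section 5.8.
- **Section 5.8:** replace the 1-month and 3-month abstinence minimums with 180 days, to match the other methods.
- **Optional:** ask about pregnancy at the existing monthly follow-up contacts, which Section 8.7 allows by phone. At nominal 30-day spacing, three contacts (days 120, 150 and 180) fall in the uncovered period; the calendar allows ±14 days on each.

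**Cost.** Wording changes in two sections, IRB notification and review as local requirements dictate (Section 16.1), possible updates to the consent form and Pregnancy Form, and outcome follow-up for any additional pregnancy reported. No new visits or tests are needed.
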